Ginger is a spice with a long history of traditional use for symptoms of a cold, including digestive discomfort, cough, and aches and pains. Clinical research shows that Ginger supports health through its benefits to the immune and respiratory systems, as well as promoting normal cytokine balance. [21, 24, 28, 29, 33]

Turmeric is a spice with a long history of traditional use for symptoms of a cold. Clinical and preclinical studies have shown it to support the immune & respiratory systems and support normal cytokine balance. Turmeric is used traditionally for wide uses, and as the research builds it shows that it is indeed capable of supporting multiple body systems, substantiating the tonic effect of this herb in maintaining overall health and vitality. [1, 15, 36]

Zinc is an essential mineral important for numerous physiological processes, notably, healthy immune response. Zinc has also been found to support immune health through a number of preclinical and clinical studies. In one study involving 100 people, zinc supplementation resulted in significant immune support. In another trial, supplementation with a zinc lozenge showed a significant decrease in the duration of cold symptoms. [6, 7, 9, 19, 20, 22, 34, 35]

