2.2.3. Minimization of Risks

Research participants will be carefully screened to meet enrollment criteria. Participants meeting exclusion criteria will not be enrolled. The study participant informed consent will be presented with clear description of the study requirements and opportunity to have questions answered before enrollment will be provided. Once an event occurs, review of symptoms will be

ascertained daily until symptoms have resolved or for 18 days. Reporting of adverse events will be reviewed routinely and in accordance with regulatory guidelines (21CFR, GCP) by the Principal Investigator. Participants with occurrence of worsening symptoms or adverse events will be advised to stop the product and may seek medical attention and exit the study.

3. Study Objectives

The purpose of the present study is to evaluate 1) the impact of the Immune Support test product on the duration of symptoms of the common cold in adult participants and 2) the subjective experience of these participants related to general health, common cold symptoms, and personal experience with the product. [13, 18, 29, 32]

This will be evaluated based on the primary and secondary endpoints. These endpoints, the analysis populations, and their respective measures are described below. Further details on the methods for measuring the outcomes can be found in the Study Outcome Measures and Analysis Plan sections.

Primary Endpoint:

The primary endpoint will be time to freedom from cold symptoms, with the clock starting at the onset of the cold. Where the onset is defined as the point in time when the participant experiences 2 or more cold symptoms. The primary analysis will be a Kaplan-Meier analysis of time to absence of all symptoms, based on the participants' self-report. There is no control group for the primary analysis. [5]

Secondary Endpoint:

- Secondary endpoints involve the duration and severity of the separate cold symptoms.
- Comparison against the participant's normal behavior.
- Net Promoter Score.
- Adverse events will be summarized.
- An additional data presentation will consist of results from both Treatment and Control in similar studies appearing in the literature. There will be no formal statistical comparison of results from this study and historical studies.

4.Study Design

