The present study will be a single site, prospective, single arm observational study of minimal risk consisting of at least 200 participants who suffer from cold symptoms. The participants must meet additional inclusion/exclusion criteria (see Inclusion/Exclusion Criteria). Participants will begin taking the powder drink-mix at the onset of their cold symptoms. Onset is defined as the point in time the participant experiences 2 or more cold symptoms (cough, hoarseness, muscle ache, nasal drainage,

nasal congestion, scratchy throat, sore throat, sneezing, or an oral temperature greater than 37.7 °C (99.9 °F)). When the participant experiences 2 or more symptoms, they will report symptoms in the cold start form. If they meet the criteria for a cold, they will start completing the daily cold symptom diary prior to taking the test product. After consuming the product, the participant will complete the cold symptom diary daily until all symptoms resolve. Since none of the ingredients in the test product have been seen to provide relief from fever or pain, the participant will be allowed to take a pain reliever and fever reducer (e.g. ibuprofen or acetaminophen). If medication is taken, the participant will record this in their symptom diary.

Study enrollment and management will be decentralized, where participants do not visit an investigator or a clinic for clinical assessment. The participants will participate in the study at home. All data collected from during this study will be reported by the participant via eCRFs, eDiary, and other electronic data entries. If a visit is required, it will be conducted via remote contact by telephone.

4.1.Test Product

Overview:

Participants in this study will consume the test product twice a day (4-6 hours apart) at the onset of cold symptoms. The participant will mix one packet of the test product in 6-8 ounces of water. The test product will be delivered to the participants' residence in a single shipment consisting of an18-day supply (36 packets) of the test product. The study participant will mix the contents of the packet into 6-8 oz. of hot water and drink twice a day during the duration of the cold.

Below is the description of the test product and its ingredients.

Test Product

Description: Combining whole food sourced Vitamin C, Echinacea, Ivy Extract, Zinc, Ginger and Turmeric. This formula is designed to support the immune system while reducing the duration of cold.

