4.2. Required Behavior

If the participant is prescribed antibiotics or any other medications for any reason, they should report this prescription and they will be withdrawn from the trial as of the prescription date.

Participants are asked not to ingest or take any other form of cold remedy (over-the-counter (NyQuil/Dayquil/Cough Syrup/Cough Drops/EmergenC/Airborne/Zarbee's or any similar cold-relief product or prescription drugs) during the 18-day study period. If taken during the study duration the participant will record this as part of their diary and will be exited from the study.

Because none of the active ingredients are aimed at pain relief or reducing fever, participants will be allowed to take pain relievers/fever reducers (Advil/Tylenol or their equivalent).

Participants are asked to limit the consumption of alcohol beverages to less than or equal to two drinks per day and avoid recreational drugs or use of cannabis during the study period.

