- At time of enrollment, participant will be given access to the HIPAA compliant study portal.
 - The study portal provides access to study information, signed informed consent form, instructions for product use, frequently asked questions, study surveys, symptom diary, and data collection tools.
- Participant shall complete baseline assessments upon access to the portal.
 - Baseline assessment will include questions regarding the participants' demographics, medications, detailed information regarding previous colds, including treatment.
- To ensure that baseline assessments are completed before test product is used by the
 participant, study materials and study welcome package will be shipped to the participant once
 the clinical study manager/clinical operations coordinator confirms that the baseline assessment
 has been completed.
- The welcome package will include an information sheet that will outline instructions for their participation in the trial, the test product, disposable thermometer, and paper forms of the

- documents (paper form of study documents will be provided for real time data collection, in the event that the participant cannot log into the study portal to input data).
- Once the participant receives the test product, the participant will log into the study portal to acknowledge the receipt of the test product.
- Study start date will be the date of acknowledgement of receipt of test product.
- Participant will be sent weekly email reminders that remind them of their participation in the study. Once the participant indicates they are experiencing a cold. The participant will be reminded by email daily to complete their symptom diary.
- At the onset of their cold symptoms, the participant will complete the cold start form.
 - Onset is defined as the point in time the participant experiences 2 or more cold symptoms (cough, hoarseness, muscle ache, nasal drainage, scratchy throat, sore throat, sneezing, oral temperature greater than 37.7°C (99.9 °F)).
 - If fever is a symptom that the participant experiences, they will use the provided disposable thermometer to take their temperature and record it in the diary.
- If the participant meets all the criteria for a cold, they will start their symptom diary prior to taking the test product.
- After completing the surveys, the participant will take the test product. The participant will mix 1 drink-mix packet into 6-8 oz of water and consume the whole drink.

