7.3. Analysis Plan

Time-dependent variable analysis

The primary analysis involves time dependent variables. The Kaplan-Meier algorithm will be used to analyze time to freedom from cold symptoms. Data presentation will include tables and graphs; in particular tables of participants at risk at various time points.

Censoring:

- Participants who do not have a cold during the trial will not be in the ITT population, and will
 not be included in the endpoint analysis.
- Participants who report the onset of a cold, but who do not complete the daily reports through
 18 days will be censored as of the date of the last report.
- Participants who still have cold symptoms at 18 days will be censored at that time.
- Participants will also be censored if they withdraw from the trial.

Secondary Endpoints:

- Analysis of the individual cold symptoms will be a presentation of median time until the
 individual symptom resolves. The median for this purpose is the value computed as part of
 the Kaplan-Meier algorithm.
- An additional analysis will investigate the relation between baseline age and gender, and the time to resolution.
- Adverse events will be summarized.
- An additional data presentation will consist of side by side presentation of results from both

Treatment and Control in similar studies appearing in the literature. There will be no formal statistical comparison of results from this study and historical studies.

General statistical methods:

Data will be analyzed using standard statistical methods, as further specified in a statistical analysis plan (SAP), which will be prepared in detail at a later date. [23]

- Data analysis will largely consist of summary statistics and graphs. The only formal statistical comparisons will be in covariate analyses.
- For continuous variables data presentation will consist of means, confidence intervals computed using the *t*-statistic, medians, and interquartile ranges. Group comparisons will use *t*-tests or ANOVA.
- For discrete variables confidence intervals will use the exact intervals, where available. Group comparisons will use Fisher's exact test, with the Monte Carlo version used where computationally necessary.
- For time to event variables analysis will use the Kaplan-Meier algorithm, and group comparisons will use the log-rank or proportional hazards methods, depending on the data type.
- Covariate analyses will investigate the relation between baseline and outcome variables, using

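### Carry-over from a permitted pain or fever reducer can date recovery too early, and the diary as worded cannot identify the entries affected

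*Combined protocol and SAP*

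**What the plan says.** Section 4.2 permits pain relievers and fever reducers: "Because none of the active ingredients are aimed at pain relief or reducing fever, participants will be allowed to take pain relievers/fever reducers". Section 4 gives much the same reason ("Since none of the ingredients in the test product have been seen to provide relief from fever or pain") and adds: "If medication is taken, the participant will record this in their symptom diary". Neither section limits amount, frequency or timing. Other cold remedies, by contrast, lead to exit from the study (section 4.2; Appendix E, item 10).

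The primary endpoint in section 3 reads: "The primary analysis will be a Kaplan-Meier analysis of time to absence of all symptoms, based on the participants' self-report". Sections 4.3 and 6.1 end participation once symptoms have resolved, or at 18 days if that is sooner. No symptom-free run is required.

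The Appendix E diary scores eight symptoms from 0 to 3. Muscle aches are item 3 and sore throat is item 7. The form is to be completed before the test product or any allowed medication. Item 9 asks whether a pain or fever reducer was taken on the current day, why, and whether it worked.

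Section 7.3 states: "The Kaplan-Meier algorithm will be used to analyze time to freedom from cold symptoms". It also plans a Kaplan-Meier median for each symptom. Its censoring rules cover participants with no cold, incomplete reports, symptoms persisting at day 18, and withdrawal. Its covariates are age, gender and baseline medications. Nothing in it uses pain-reliever intake recorded during the cold.

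**The concern.** The permission is justified by what the product is thought to do. What matters for the analysis is what the endpoint measures, and two scored symptoms are of the kind these medicines are taken for. If such a symptom is suppressed when the diary is completed and everything else has cleared, the entry is all zeros. The participant is then counted as recovered and leaves, so a return of the symptom the next day is never seen.

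The error has one direction. Masking can turn a positive score into a zero but not the reverse, so the recorded time is never later than the true one. With a single arm, no control group shares the error. The results will be set beside published treatment and control arms and may inform a later two-arm trial, so an unquantified shortening would carry forward into both uses.

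**Working it through.** **The plan's own figure.** Section 7.2 expects a cold in 40% of 200 enrolled: 200 × 0.40 = 80 participants. This reproduces. No power formula applies, because the primary analysis is descriptive and single-arm.

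**How a masked entry arises.**
1. A dose taken after today's diary cannot affect today's scores if the Appendix E order is followed.
2. A dose taken later that day or overnight may still be acting when the next diary is completed. This is the carry-over route.
3. A participant may also take the dose first and complete the diary afterwards. Section 11 acknowledges that compliance has no independent check.

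**Whether the diary would show it.** Suppose a dose is taken on the evening of day 4, after that day's form. The day 4 form was completed before the dose, so item 9 is answered no. The day 5 form asks about day 5 only and is again completed before medication, so item 9 is no again. The dose appears on neither form. No dose time is requested, so even a yes cannot be placed before or after the scores. Item 9 also asks whether the medicine worked, which presupposes that dosing came first and conflicts with the form's own instruction.

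**When it matters.**
- Primary event: only if a pain-type symptom is the last to clear. Nothing in the documents says a pain reliever clears cough, sneezing or nasal symptoms.
- Muscle-ache and sore-throat medians: exposed whenever the item is masked, whatever the other symptoms are doing.

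**Possible size, on assumptions only.** The documents give no symptom durations and no usage rates. A simple range takes a pain-type symptom as last to clear in 10% to 30% of colds, with a reducer acting at the first all-zero entry in 25% to 50% of those:
- low: 0.10 × 0.25 = 2.5%; × 80 = 2 participants
- high: 0.30 × 0.50 = 15%; × 80 = 12 participants

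A wider simulation assumed a median cold of 7 days (lognormal, log-SD 0.45, whole days). A share s of participants (10%, 25% or 50%) had only pain-type symptoms in the last L days (1, 2 or 3), with daily masking probability m (10%, 30% or 50%). Ignoring very short colds, the share recovered early is s × [1 − (1 − m)^L]:

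| s, L, m | Formula | Simulated share | Of 80 | Mean shortening | Median |
|---|---|---|---|---|---|
| 0.10, 1, 0.1 | 0.10 × 0.10 = 0.010 | 0.010 | 0.8 | 0.01 day | 7 to 7 |
| 0.25, 2, 0.3 | 0.25 × 0.51 = 0.1275 | 0.127 | 10.1 | 0.20 day | 7 to 7 |
| 0.50, 3, 0.5 | 0.50 × 0.875 = 0.4375 | 0.432 | 34.6 | 1.03 days | 7 to 6 |

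The median stayed at 7 days in 24 of the 27 combinations and fell to 6 in the three heaviest.

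**The case against.** The strongest reply is that Appendix E already guards against this by having symptoms scored before any allowed medication. That stands in part: a reader might infer that any day made symptom-free by a painkiller counts as recovery, and with the order followed that is not so for a dose taken after the diary. Carry-over and departures from the order remain.

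A reader might also include fever among the masked endpoint symptoms. The documents do not settle this. Temperature above 37.7 °C is an onset criterion, and section 6.1 says of participants with fever that "they will use the provided disposable thermometer to take their temperature and record it in the diary", but the Appendix E form has no temperature item. On the form as written, fever is not scored for resolution.

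A third reply is that self-reported recovery with permitted background medication is a legitimate target for a descriptive study with no formal historical comparison. That stands, and it is why the documents do not support a claim that the primary event is wrong and must be redefined. Making any recorded use block recovery would also delay recovery for people who took a tablet for an unrelated reason and, because section 6.1 ties dosing to the daily diary, could prolong product use.

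Finally, section 7.3 defers detail to a later SAP, so an analysis rule can still be added. The diary wording cannot wait, because data collected under the present item 9 would not support the analysis.

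**Conclusion.** The concern holds in limited form. Pain and fever reducers are allowed without a stated limit, pain-type symptoms are scored, one all-clear ends follow-up, and no rule uses recorded intake. Any masking by carry-over or by dosing before scoring therefore shortens the estimate, and the plan can neither detect nor bound it.

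The size is unknown. The figures of 2 to 12 and about 1 to 35 of 80 rest entirely on assumed rates and should not be read as estimates. They suggest that the overall median would often not move, while the muscle-ache and sore-throat medians are more directly exposed. This warrants a diary correction and a sensitivity analysis, not a change of primary endpoint. Whether these medicines should be permitted is a clinical matter and is not judged here.

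**What to change.** Keep the primary event as it is, and:

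1. Reword diary item 9 to ask about pain or fever reducer use since the previous diary, add the time of the last dose, and keep the existing question on the reason. Do this before data collection.
2. In section 7.3, prespecify a sensitivity analysis for the primary event and for the muscle-ache and sore-throat medians. An all-zero (or item-zero) entry with cold-related use since the previous diary is not an event. Either censor the participant there or, if diary-only follow-up continues, take the next medication-free zero entry as the event. Censoring is simpler but probably informative, since those censored are likely to be near recovery, so the result would tend to err towards longer colds.
3. State that any extra diary days do not alter the product-use rules.
4. Report the number of resolution entries with recorded use.

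Separately, reconcile two conflicts. Sections 4 and 4.2 deny pain relief from the ingredients, while section 2.1 says "Ginger is a spice with a long history of traditional use for symptoms of a cold, including digestive discomfort, cough, and aches and pains" and reference 24 is a trial of ginger for pain relief. Section 6.1 has temperature recorded in the diary, while Appendix E has no place for it.

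The cost is slightly longer diary wording, one extra analysis, and possibly one or two more diary days for some participants.

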4.3. Participation Period

Participants are expected to participate in the study for 18 days after the onset of the first cold. Onset is defined as the day that the participant experiences 2 or more cold symptoms. Participant will be exited once all symptoms have been resolved or at 18 days whichever is shorter. If no cold has started within 90 days of participant study start date (date the participant receives and records receipt of test product) participants will be exited from the study.

4.4. Data Collection

All data in the present study will be self-reported by the participant and collected via their online portal (Hawthorne Effect Study Visit Management System (HE VMS). Participants will be asked to take the test product according to the instructions for use, complete study surveys and respond to study reminders during the course of the study. The instructions for use and study forms can be found in the appendix.

The primary endpoint will be time to freedom from cold symptoms, with the clock starting at the onset of the cold. The primary analysis will be a Kaplan-Meier analysis of time to absence of all symptoms, based on the participants' self-report. There is no control group for the primary analysis.

Secondary endpoints involve evaluation of the duration and severity of the separate cold symptoms. An additional data presentation will consist of results from both Treatment and Control in similar studies appearing in the literature. There will be no formal statistical comparison of results from this study and historical studies.

5. Study Population

5.1. Selection of the study Population

The study population will consist of at least 200 participants who have completed the self-enrollment form and who meet the inclusion-exclusion criterion. The participants will otherwise be in good health.

The target sample size for this study is initially 200 participants, with a desired sample of 80 treated participants This sample size has been calculated to provide a reasonable estimate of the time to cold resolution, as further described in detail in the Statistical Considerations section.

At such time as 180 participants have been enrolled, the available data will be analyzed using a constant hazard model to determine if it seems realistic that the desired number of 80 treated participants will be met by the end of follow-up. If the expected number of treated participants is less than 80, the target sample size will be increased as needed, considering both the desire for 80 treated participants and the timelines of the trial sponsor. The actual outcomes of treated participants will not be considered in this analysis, merely whether or not enrolled participants have reported starting using the test product.

Enrollment will be stopped once the target number of participants have been enrolled; no further participants will be offered a place in the trial once the target sample size criteria has been met. All participants who have already been offered places, but who have not yet consented, will be allowed to participate as long as they have signed the study consent within 15 days and the total number of participants does not exceed 125% of the target (either 200 or the recomputed target if recomputation has been performed).

In order to ensure an age and sex distribution that is reasonably representative of the US population, enrollment may be stopped early in some age and sex groups.

Target population for this study are candidates who are in the general population who are seeking herbal remedies to reduce the duration of their common cold symptoms.

Participants will be enrolled from across the United States. No participants will be enrolled outside of the United States. It is expected that the geographical distribution of the participants enrolled in the study will correlate with the geographical distribution of the general population across the United States.

Participants will be recruited via digital advertisements. Ads will target those who are prone to getting the common cold; travelers, healthcare providers, teachers, daycare workers, etc.

After clicking on an advertisement, potential participants will then be directed to a website where they will complete a screening questionnaire (See Appendix). The screening questionnaire will

automatically qualify or disqualify them for study participation. If the participant qualifies, she will be provided an informed consent. Upon completion of the informed consent they will be deemed enrolled in the study.

5.2.Inclusion/Exclusion Criteria

Prior to being enrolled, participants will fill out a screening questionnaire. The screening questionnaire will automatically qualify or disqualify them for study participation. The full screening questionnaire can be found in the Appendix.

Inclusion Criteria:

Adult candidates in the general population who are in good health and are seeking herbal remedies to reduce the duration of their common cold symptoms when they should arise. Participants will be deemed to be in good health if they do not report any of the medical conditions asked about in the screening questionnaire.

Exclusion Criteria:

- Age < 18 years old
- Unwilling to try the test product during their first cold experience in the trial
- Has any of the following medical conditions:
 - Allergy to any of the following ingredients: Echinacea, Ivy Extract, Camu Camu, Vitamin C, Ginger, Turmeric, Zinc or a known allergy to Guar Gum, Monk Fruit, Citric Acid, Natural Flavors.
 - Alcohol consumption more than 10 drinks per week
 - Chronic renal disease
 - Chronic liver disease
 - Known autoimmune or immunodeficiency disorders
 - Pregnant or breastfeeding

6.Study Evaluation

6.1.Study Procedures

- Candidates will review information about the study and complete a screening form.
- During the screening process, the participant will be asked questions regarding their symptoms and medical history to ensure that they meet the requirements to participate in this study. The potential participant will also be asked questions to ensure that they do not meet any of the exclusion criteria and meet all of the inclusion criteria.
- After successful screening (participant does not meet any exclusion criteria), participants will
 review and sign study informed consent.
- Upon verification of signed informed consent, participant will be enrolled into the study.
- At time of enrollment, participant will be given access to the HIPAA compliant study portal.
 - The study portal provides access to study information, signed informed consent form, instructions for product use, frequently asked questions, study surveys, symptom diary, and data collection tools.
- Participant shall complete baseline assessments upon access to the portal.
 - Baseline assessment will include questions regarding the participants' demographics, medications, detailed information regarding previous colds, including treatment.
- To ensure that baseline assessments are completed before test product is used by the
 participant, study materials and study welcome package will be shipped to the participant once
 the clinical study manager/clinical operations coordinator confirms that the baseline assessment
 has been completed.
- The welcome package will include an information sheet that will outline instructions for their participation in the trial, the test product, disposable thermometer, and paper forms of the

- documents (paper form of study documents will be provided for real time data collection, in the event that the participant cannot log into the study portal to input data).
- Once the participant receives the test product, the participant will log into the study portal to acknowledge the receipt of the test product.
- Study start date will be the date of acknowledgement of receipt of test product.
- Participant will be sent weekly email reminders that remind them of their participation in the study. Once the participant indicates they are experiencing a cold. The participant will be reminded by email daily to complete their symptom diary.
- At the onset of their cold symptoms, the participant will complete the cold start form.
 - Onset is defined as the point in time the participant experiences 2 or more cold symptoms (cough, hoarseness, muscle ache, nasal drainage, scratchy throat, sore throat, sneezing, oral temperature greater than 37.7°C (99.9 °F)).
 - If fever is a symptom that the participant experiences, they will use the provided disposable thermometer to take their temperature and record it in the diary.
- If the participant meets all the criteria for a cold, they will start their symptom diary prior to taking the test product.
- After completing the surveys, the participant will take the test product. The participant will mix 1 drink-mix packet into 6-8 oz of water and consume the whole drink.
- Participant will take the test product twice a day, at least 4-6 hours apart.
- The next day the participant will complete their symptom diary prior to taking the test product. Once completed they will mix 1 packet of the test product into 6-8 oz of water and consume the whole drink. They will take the test product again 4-6 hours later.
- The participant will complete this process daily until their cold symptoms resolve or for 18 days, whichever is shorter.
- If the participant takes ibuprofen or acetaminophen at any time, the participant will record this on their symptom diary.
- After taking the test product, the participant will be instructed to fill out an Adverse Event form for any side-effects experienced.
- The participant will be prompted, by email, to complete the study exit form once the participant's symptoms resolve completely or after 18 days, whichever is shorter.
- Neither the sponsor nor Hawthorne Effect, Inc. will make any attempt to collect any unused test product.
- Upon receipt of study exit survey and review of completed study forms, participant will receive an Amazon gift card of \$25 via email.

6.2.Study Schedule of Activities

Assessments	Screening	Consent	Before Receipt of Test Product	Product Received	Event Start Date**	Days 1-18*	Study Exit***
Study Window							
Screening Survey	Х						
Consent		Х					
Baseline Survey			х				
Demographics			х				
Acknowledgement of Receipt of Test Product				Х			
Test Product Consumed****					Х	Х	
Symptom Diary					Х	Х	Х
Meds & Supplements			Х				
AE Assessment					Х	Х	Х
Study Exit Survey							Х

^{*}Participant will participate in the study starting on the day of the cold until the cold symptoms resolve or 18 days whichever is shorter.

^{**} The day the participant experiences 2 or more of the protocol defined symptoms

^{***} The participant will exit the study at the time of complete cold symptom resolution, 18 days after the start of cold symptoms, or at 90 days if no cold is experienced by the participant.

^{****} The product will be consumed twice a day, 4-6 hours apart

